3.1.2 Dose Escalation in Phase I Portion

The initial dose of mithramycin administered in the Phase I portion is 74% of the phase II dose which equals 13 mcg/kg/dose, to be repeated every 28 days. Once safety of the starting dose is established, mithramycin will be escalated to the dose of 17.5 mcg/kg/dose according to the following table.

This limited proposed dose escalation is shown below:

Dose Level	Dose (mcg/kg/dose)	Percent change
-1	9.0	-31%
1	13	0
2	17.5	35%

All patients will receive dexamethasone as described in Section 4.3.

Cohorts of 3 to 6 patients will be treated at each dose level. Toxicity will be graded using version 4.0 of the NCI Common Toxicity Criteria, and the MTD will be defined based on toxicities observed during the first treatment cycle. When a minimum of 3 patients who are evaluable for toxicity have completed 1 cycle of therapy without evidence of DLT, subsequent patients may be enrolled at the next higher dose level. If DLT is observed in 1 patient from the initial cohort of 3 patients, up to an additional 3 patients will be entered at that dose level. If none of these additional patients experiences a DLT (1/6 with DLT), the dose will be escalated. If ≥ 1 of the additional patients experience a DLT ($\geq 2/6$ with DLT), the MTD has been exceeded. If the MTD has been exceeded at the first dose level, then the subsequent cohort of patients will be treated at dose level -1. If $\geq 2/6$ patients experience DLT at the -1 dose (9.0 mcg/kg/dose), no further patients will be enrolled until completion of discussions with the sponsor, FDA and NCI IRB and approval of a protocol amendment.

The MTD will be the maximum dose at which fewer than one-third of patients experience DLT during cycle 1 of therapy.

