3.1.1 Dose Limiting Toxicity

Dose limiting toxicity (DLT) will be defined as non-hematologic toxicity and hematologic toxicity. Toxicities observed during the first treatment cycle will be used to determine the MTD. For the Phase II portion of the study, the below toxicities will be considered treatment limiting.

- **Non-hematologic DLT** will be defined as any grade ≥ 3 non-hematological toxicity possibly, probably, or definitely related to mithramycin with the exception of:
 - Grade 3 nausea that is controlled by symptomatic treatment with anti-emetics within 72 hours.
 - Grade 3 vomiting that is controlled by symptomatic treatment with anti-emetics within 72 hours.
 - Grade 3 diarrhea that is controlled by symptomatic treatment within 72 hours.
 - Asymptomatic grade 3 elevation of serum transaminases that return to \leq grade 1 within 14 days of completing mithramycin administration during a cycle.
 - Asymptomatic grade 3 electrolyte abnormalities that are correctable to grade 2 or less within 48 hours.
- **Hematologic DLT** will be defined as:
 - Grade 4 neutropenia (ANC $< 500/\text{mcL}$) on two consecutive blood counts drawn at least 72 hours apart in patients receiving prophylactic growth factor support (See Section 3.4) or
 - Grade 4 thrombocytopenia ($< 25,000/\text{mcL}$) refractory to platelet transfusion*.
 - Failure to recover platelet count to $\geq 75,000/\text{mcL}$ by day 42 of starting a treatment cycle.
- Any grade 2 bleeding not promptly (within 6 hours of appropriate intervention) corrected with blood product support will be considered dose-limiting.
- Bleeding that does not stop within 6 hours of administration of appropriate treatment including platelets, will be considered DLT and mithramycin will be discontinued.
- Any grade 2 mithramycin related toxicities of ≥ 7 days may be considered dose limiting if they are intolerable to the patient and cannot be controlled with standard supportive measures.
- Failure to recover from toxicity within 42 days of starting a treatment cycle to the level required for initiating subsequent cycles (Section 3.4) will be considered dose-limiting

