4 CONCOMITANT MEDICATIONS AND SUPPORTIVE MEASURES

4.1 MANAGEMENT OF BLEEDING, HEMATOLOGIC AND BLOOD PRODUCT SUPPORT

Blood product support should be provided to maintain platelets $\geq 25,000$ cells/mcl and as clinically indicated.

Growth factor support to patients who experience grade 4 neutropenia (ANC $<500/\mu\text{L}$) will not be administered prophylactically, but may be administered as defined in Section 3.3. In addition,

growth factor support may be administered to patients who develop grade 4 neutropenia if clinically indicated, for example in patients who develop sepsis.

If patients experience any signs of bleeding (\leq Grade 2) including, epistaxis, hematuria, hematemesis or blood in the stool, the patient will immediately undergo a comprehensive clinical evaluation, coagulation profile including PT/PTT/fibrinogen, thrombin time, PFA-100, D-dimer, and comprehensive metabolic panel including Ca^{2+} and ionized calcium. Any abnormality will be corrected as clinically indicated with blood product support with guidance by hematology (NIH CC hematology consult). If a patient experiences bleeding in the setting of a normal platelet count, platelet function tests will be performed and the patient should be transfused with platelets even in the presence of a normal platelet count while these studies are pending. Mithramycin has also been known to block SP1, and SP1 has been shown to play a role in the expression of GPIIb. Therefore, mithramycin may cause a deficiency in this protein in mature platelets theoretically mimicking the bleeding diathesis, Glanzmanns thrombasthenia (45).

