8.6 NUMBER AND RATE OF ACCRUAL

If a maximum of 18 patients are required to complete the phase I portion, and 9 to 24 patients are required to complete the phase II portion, the maximum number of evaluable patients required to complete both portions of this trial is 42.

With an estimated monthly accrual of 1-2 patients, the projected duration of this study is 2 to 3.5 years.

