9.3 EVALUATION OF BENEFITS AND RISKS/DISCOMFORTS

Patients under the age of 18 years will be entered on this trial. The primary risk to patients participating in this research study is from toxicity of mithramycin, an investigational agent in this patient population. The protocol provides for detailed and careful monitoring of all patients to assess for toxicity and the dose escalation scheme is very conservative. Toxicity data from the current dose level will be collected and reviewed to ensure that there were no severe (dose-limiting) toxicities prior to escalating to the next higher dose level. Although the primary objective

of the phase I portion of this trial is to define the qualitative toxicities and maximum tolerated dose of the drug, all patients entered on the trial will have refractory or recurrent disease, which this agent may benefit. Patients enrolled on the phase II portion of the study will be diagnosed with Ewing Sarcoma Family of Tumors with EWS-FLI1 fusion transcript, for which laboratory data suggested this agent may be of benefit. Mithramycin offers a potential for direct benefit although the likelihood of this may be small. The potential benefits from this therapy are disease stabilization or shrinkage and a reduction in symptoms caused by the tumor. Therefore, this protocol involves greater than minimal risk, but presents the potential for direct benefit to individual subjects.

Mandatory serial tumor biopsies will be obtained in participants with Ewing sarcoma with EWS-FLI1 fusion transcript who are 18 years of age or older, who have disease amenable to biopsy as outlined in Section **Error! Reference source not found.**. Risks include risk of bleeding, bruising, pain or rarely, infection.

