11.3 APPENDIX 3: STUDY CALENDAR

Procedure^p	Screening/ Baseline^{**}	Cycle 1 (28 Days) and subsequent cycles													Post Therapy Follow-up
		Day 1	Day 2	Day 3	Day 4	Day 5	Day 6	Day 7	Day 8	Day 9	Day 10	Day 14	Day 21	Day 28	
History, PE ^a	X	X ^a						X ^a				X ^a	X ^a	X ^a	
Weight ^{aa}	X		X	X	X	X	X	X							
Height (baseline only)	X														
Vital signs (BP, HR, RR, temp)	X	X	X	X	X	X	X	X							
Performance Score	X														X
Histologic Path confirmation	X														
• CBC, differential															
• sodium, potassium, chloride, CO ₂ , creatinine, glucose, BUN, albumin, calcium, magnesium, phosphorus, uric acid LDH and (amylase, lipase, baseline only)															
• alk phos, ALT/AST, T bilirubin, Direct bilirubin, T protein															
• Plasma sample (1mL) ^c		X ^c													
• PT/PTT, Thrombin Time, Fibrinogen ^d	X ^d	X ^d		X ^d	X ^d	X ^d		X ^d	X ^d	X ^d					X
• HIV, HBV, HCV ^e	X ^e														
• Pregnancy Test (urine) ^f	X ^f	X ^f													

Procedure ^p	Screening/ Baseline ^{**}	Cycle 1 (28 Days) and subsequent cycles													Post Therapy Follow-up
		Day 1	Day 2	Day 3	Day 4	Day 5	Day 6	Day 7	Day 8	Day 9	Day 10	Day 14	Day 21	Day 28	
• Urinalysis	X ^{ff}	X ^{ff}													
• Coags: , PFA-100, VWF antigen, VWF activity, Factor VIII activity, D-dimer, fibrin degradation products, FXIII activity	X														
Mithramycin infusion		X	X	X	X	X	X	X							
Receive oral/IV dexamethasone ^o		X	X	X	X	X	X	X	X						
MUGA or echocardiogram	X														
12-lead EKG ⁿ	X	X			X ⁿ			X							X
Radiological Assessments: CT, MRI, FDG-PET, Bone scan ^g	X												X ^g		X
Pharmacokinetics ^h		X ^h	X ^h		X ^h			X ^h	X ^h (and D9)						
Serum Pharmacodynamic Marker ⁱ		X ⁱ													
Mandatory biopsy for NR0B1 expression ^j	X ^j				X ^j										
Adverse Events ^k		X													X
Concomitant Medications ^l		X													X

**Blood tests within 7 days prior to enrollment; imaging studies within 2 weeks prior to enrollment (UNLESS otherwise stated), histological path evaluation is recommended to be completed prior to arrival

^aWeekly during active treatment, and weekly until recovered from toxicity.

^{aa}Daily weight recommended for days 2-7 of mithramycin infusion.

^bDaily on days 2 through 7, then twice weekly days 9 to 28 of cycles 1 through 3

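### Section 3.1.2 lets the dose rise after one 28-day cycle, although the recovery DLTs in 3.1.1 are not decided until day 42

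*Combined protocol and SAP*

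**What the plan says.** **Escalation trigger.** Section 3.1.2 applies a 3+3 rule. Once at least three children evaluable for toxicity "have completed 1 cycle of therapy without evidence of DLT, subsequent patients may be enrolled at the next higher dose level". The MTD rests on DLTs in the first cycle. Treatment repeats every 28 days (3.1.2), with a 2-day tolerance either way (3.2), and Appendix 3 heads the cycle as 28 days.

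**Recovery DLTs.** Section 3.1.1 counts as dose-limiting "Failure to recover from toxicity within 42 days of starting a treatment cycle to the level required for initiating subsequent cycles". Section 3.4 sets that level at ANC 1000/mcL and platelets 75,000/mcL, plus the other eligibility laboratory values. A separate bullet requires platelets to be back at 75,000/mcL "by day 42 of starting a treatment cycle".

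**Neutropenia on counts.** The grade 4 criterion in 3.1.1 applies only "in patients receiving prophylactic growth factor support". Section 4.1 says growth factor "will not be administered prophylactically, but may be administered as defined in Section 3.3", and 3.3 allows it from the next cycle, after a grade 4 episode that has recovered.

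**Assurance.** Section 9.3 says toxicity data at the current dose are reviewed "to ensure that there were no severe (dose-limiting) toxicities prior to escalating to the next higher dose level".

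**The concern.** The escalation trigger and the DLT definition run on different clocks. A child with ANC 400/mcL and no complication on day 28 has finished a 28-day cycle and has no DLT by definition. The one criterion that covers this child is settled only on day 42. A child with platelets of 40,000/mcL on day 28 who still responds to transfusion is in the same position.

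Two things are at stake. The next children may be enrolled at 17.5 mcg/kg while a protocol-defined DLT at 13 mcg/kg is still open, which is what 9.3 says will not happen. And because the MTD uses first-cycle toxicity, two teams could disagree on whether a DLT declared between days 29 and 42 enters the count that sets the pediatric dose.

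**Working it through.** The plan gives no figure to reproduce here. The check sets the rules side by side and then sizes the gap.

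**Step 1: which criterion covers uncomplicated cycle-1 neutropenia?** The count-based bullet needs prophylactic growth factor (3.1.1). That is excluded except under 3.3 (4.1), and 3.3 first allows it in the next cycle. The bullet therefore cannot be met in cycle 1. Growth factor given as treatment, for example in sepsis, is neither prophylactic nor an uncomplicated case. What remains is the 42-day recovery rule.

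**Step 2: length of the gap.** 42 − 28 = 14 days. With the 2-day tolerance in 3.2 it is 42 − 30 = 12 to 42 − 26 = 16 days.

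**Step 3: children exposed.** Section 8.6 states: "With an estimated monthly accrual of 1-2 patients". With 30.4 days per month, the expected number of entries in 14 days is 14/30.4 × 1 = 0.46 to 14/30.4 × 2 = 0.92. That accrual covers both portions of the trial, so these are upper values for children entering at 17.5 mcg/kg.

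**Step 4: size of the step.** 17.5/13 = 1.35, a 35% increase to the adult phase II dose. It is the only upward step.

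**Step 5: effect on the 3+3 decision.** The documents give no rate of non-recovery by day 42. Assume a rate L per child, children independent, and no other DLTs.

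- Full 42-day window: P(escalate) = (1−L)³ + 3L(1−L)⁵.
- Day-28 reading, only the last child of each cohort unresolved at the decision: P(escalate) = (1−L)² + 2L(1−L)⁴. A first-cohort DLT is taken as visible by the end of the second cohort.
- Same reading, probability of escalating with a DLT still open: L(1−L)²[1 + 2L(1−L)²].

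| Assumed L | P(escalate), 42 days | P(escalate), day 28 | Difference | P(escalate with an open DLT) |
|---|---|---|---|---|
| 2% | 0.995 | 0.997 | 0.002 | 0.020 |
| 5% | 0.973 | 0.984 | 0.011 | 0.049 |
| 10% | 0.906 | 0.941 | 0.035 | 0.094 |
| 20% | 0.709 | 0.804 | 0.095 | 0.161 |

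Worked at L = 10%: 0.729 + 0.3 × 0.590 = 0.906; 0.81 + 0.2 × 0.656 = 0.941; 0.1 × 0.81 × (1 + 0.2 × 0.81) = 0.094.

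If all three children reached day 28 together, the open-DLT probability would be 1 − (1−L)³ = 0.059, 0.143, 0.271 and 0.488. At one to two patients a month over both portions, that is the less likely case. Adding an independent 10% rate of earlier DLTs lowers the last column to 0.018, 0.042, 0.078 and 0.125.

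**The case against.** The best defense is that day 28 is not the intended end of cycle 1. Section 3.1.1 lists day-42 non-recovery as a DLT and bases the MTD on first-cycle toxicity. If cycle 1 always closed on day 28, those DLTs could never count. On that view a cycle runs until the next one may start, or to day 42. This is a sensible intent and may well be what the team would do, but 3.1.2 does not say it, and the stated cycle length points the other way.

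The plan also leaves room for judgment. The trigger in 3.1.2 is permissive and follows a statement that safety of the starting dose must first be established. Section 7.5.1 has the team meet every two weeks while patients are on treatment, and 9.3 promises a review. An unrecovered child would be known to those reviews. That stands as a partial safeguard. But none of these sections sets a waiting period, and on day 28 the reviewers would find no DLT because none has yet been defined.

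A reader might infer from the Appendix 3 footnote, "then twice weekly days 9 to 28 of cycles 1 through 3", that counts stop on day 28. The documents do not support that. Section 3.5.1 asks for twice-weekly counts throughout cycles 1 to 3 with no day-28 stop, and 3.5.2 continues weekly counts after treatment ends, until recovery or stabilization.

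A reader might also infer that a late DLT is lost. The 3+3 rules carry no day-28 cut-off, so a DLT confirmed on day 42 can still trigger more children at that dose. What is missing is a rule for children already enrolled at 17.5 mcg/kg.

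**Conclusion.** The point holds as a defect in the escalation rule, small in size but worth correcting. Following 3.1.2 as written, the one step from 13 to 17.5 mcg/kg can be taken up to 14 days before a recovery DLT is decided, and the status of a day 29 to 42 DLT for the MTD is unclear. This rests on reading one cycle as 28 days, which 3.1.2, 3.2 and Appendix 3 support.

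On average at most about 0.5 to 0.9 children would enter in the window. With only the last child unresolved, P(escalate) rises by 0.2 to 3.5 percentage points at assumed non-recovery rates of 2% to 10%, and by 9.5 points at 20%. These rates are assumptions.

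Three stronger readings are not supported:

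- **Expansion and pediatric phase II entry.** A reader might extend the day-28 trigger to both. The clause governs only enrollment at the next higher dose. Pediatric phase II entry depends on the dose having been determined and judged safe, with no day-28 clock.
- **Wrong escalation.** Escalating with an open DLT is not the same as escalating in error. One DLT in three calls for three more children, and that often still ends in escalation.
- **Tolerated neutropenia.** Not counting a first episode that recovers is consistent with the retreatment rule in 3.3 and is not at issue.

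**What to change.** Add to section 3.1.2:

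> For escalation and MTD determination, a patient has completed cycle 1 when the section 3.4 laboratory criteria are met again or on day 42, whichever comes first. DLTs declared by day 42 count toward cycle 1. No patient is enrolled at the next dose level while a pending result could change the decision.

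The DLT definition, the 3.3 retreatment rule, the monitoring schedule and the sample size stay as they are.

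There is no delay if every child in the cohort has recovered by day 28. Otherwise the escalation decision waits up to 14 days. Against the projected 2 to 3.5 years in section 8.6, that is 14/730 = 1.9% to 14/1277.5 = 1.1% of the study duration.

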3.1.3 Phase II Portion

Using a Simon two stage design (see Section 8), mithramycin will be administered intravenously at the recommended dose and schedule up to 24 patients evaluable for response. All patients will receive dexamethasone as described in Section 4.3. Initially adults (≥ 18 years of age) with Ewing sarcoma and EWS-FLI1 fusion transcript will be enrolled in order to determine the objective response rate (PR and CR) using RECIST. Once adult dose is deemed safe, children (≥ 12 months) and adolescents (≤ 17 years) with Ewing sarcoma and EWS-FLI1 fusion transcript will begin enrollment to the Phase II portion. Should the pediatric phase II dose of mithramycin differ from the adult phase II dose, the protocol will be amended to address accrual and response rate to mithramycin in children in a separate stratum.

Assessment of NR0B1 in serial tumor biopsies: Should less than 12 patients with evaluable tumor biopsies be available at the time response objectives are met, enrollment on this trial will continue for patients undergoing tumor biopsies until a minimum of 12 patients with tumor biopsies evaluable for analysis of NR0B1 inhibition have been enrolled ([Appendix 7: Studies to be performed on tumor tissue](#)).

3.2 DRUG ADMINISTRATION

Mithramycin will be administered intravenously during hospitalization for the first cycle. The dose of mithramycin will be diluted in appropriate fluids and will be infused over 6 hours daily for 7 days to be repeated every 28 days (+/- 2 days) ([Appendix 3: Study Calendar](#)). In the phase II portion, mithramycin will be administered at a dose of 17.5 mcg/kg/dose.

Intravenous hydration should be provided as clinically indicated.

3.3 DOSE REDUCTION OR MODIFICATIONS

Patients who experience a DLT (as defined in Section [3.1.1](#)) possibly, probably or definitely related to mithramycin, will have mithramycin held.

Patients may continue on study at a reduced dose (reduced one dose level as defined in Section 3.1.2), after having recovered from the experienced DLT within \leq 42 days of starting the treatment cycle.

If a patient experiences any of the following events, mithramycin will be held and no further mithramycin will be administered:

- grade 3 or 4 anaphylaxis or allergic reaction
- grade 4 DIC
- grade 4 erythema multiforme, toxic epidermal necrosis (TEN), or Stevens-Johnson syndrome
- grade 4 diarrhea
- grade 3 hemorrhage if endoscopic or operative intervention required or any grade 4 hemorrhage
- grade 2 or greater bleeding that does not resolve within 6 hours of administration of appropriate treatment
- CNS hemorrhage of any grade

For the Phase 1 portion only: Patients who initiate treatment at the -1 dose level and experience a DLT, will have a ~30% dose reduction for subsequent cycles.

For both Phase 1 and Phase 2 portions: If another DLT is observed on the reduced dose, the patient will discontinue protocol therapy permanently unless the patient is receiving benefit from mithramycin as evidenced by disease stabilization or tumor shrinkage, in which case a further dose reduction will be permitted.

Patients who experience Grade 4 neutropenia (<500/mcL) on two consecutive blood counts drawn at least 72 hours apart, who recover to meet criteria for additional cycles may receive mithramycin at full dose in the next cycle with growth factor support. If grade 4 neutropenia (<500/mcL) on two consecutive blood counts drawn at least 72 hours apart recurs with growth factor support, this will be dose-limiting (Section 3.1.1), and dosing may continue at a reduced dose of mithramycin as described above with growth factor support.

Patients who do not recover from toxicity within 42 days of starting a treatment cycle to the level required for initiating subsequent cycles (Section 3.4) will be permanently removed from treatment with mithramycin.

For the Phase 2 portion only: If 2 or more of the initial 6 patients enrolled at the 17.5 mcg/kg dose experience dose-limiting hepatotoxicity, enrollment will be put on hold until a discussion with the sponsor and IRB and possibly FDA have been held.

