The most profound toxicity seen was hemorrhage. The tendency for bleeding occurred infrequently and in early reports was attributed to thrombocytopenia and accounted for 3 deaths out of 84 patients treated (33). Subsequent studies showed that bleeding occurred early in treatment at about day 4 and was dose related occurring in 5.4% of 1150 patients treated at 30 mcg/kg/day or less (25). This time frame is significantly shorter than what is typically seen for chemotherapy induced thrombocytopenia. In addition, it appears as though the platelet count remained >20,000/mcL in most of the cases of hemorrhage in the literature. Subsequent to these studies, it was determined that mithramycin treatment caused a decrease in coagulation factors II, V, VII and X (34). In addition, subsequent studies revealed that mithramycin causes abnormal platelet adhesion in the setting of a normal platelet count consistent with a platelet adhesion

molecule deficiency (35). It is notable, that in addition to inhibiting EWS-FLI1, mithramycin is known to inhibit the SP1 transcription which is known to drive the biosynthesis of coagulation factors as well as platelet adhesion glycoproteins. Nevertheless, in all the cases of hemorrhage reported in the literature, it is not clear if the patients were taking any anti-coagulation medications, what type of blood product support was provided, and how effective the blood product support was in that era of treatment. In particular, it is not clear if patients received platelets in the setting of a normal platelet count as would be required for an acquired platelet adhesion defect. Regardless of the etiology, this side effect must be approached with extreme caution.

Another rare but significant side effect described in the literature is the report of toxic epidermal necrolysis that has been associated with mithramycin treatment (36, 37). This side effect is reported in two separate case reports but was omitted in the package insert from Pfizer (37) and appears to begin with plethora and non-specific skin findings. The incidence of this side effect is unclear, however due to the substantial nature of this reaction, all skin eruptions should be approached with significant caution.

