3 STUDY IMPLEMENTATION

3.1 STUDY DESIGN

This study will be conducted as a single institution, open label Phase I/II trial of mithramycin. The Phase I portion will be conducted in children and adolescents (12 months to \leq 17 years of age) with refractory extracranial solid tumors. The cohort at the recommended dose or MTD will be expanded up to 12 patients, and attempts will be made to enroll at least 6 patients that are \geq 12 years of age and 6 patients that are $<$ 12 years of age to gain experience with a broad age range of patients.

In the phase II portion of the trial the adult dose (17.5 mcg/kg/dose) will be administered to patients with measurable refractory or recurrent Ewing sarcoma and EWS-FLI1 fusion transcript to determine the objective response rate (CR and PR) to mithramycin using RECIST criteria. Initially this portion of the trial will be open to eligible participants \geq 18 years of age. Enrollment will be expanded to include children and adolescents once safety at this dose is determined. If the pediatric phase II dose of mithramycin differs from the adult phase II dose, the protocol will be amended to address accrual and response rate to mithramycin in children in a separate stratum.

The Phase I and Phase II portions of the protocol will enroll patients simultaneously.

Patients with ESFT enrolled on this study (phase II portion) who meet eligibility criteria for tumor biopsies will undergo mandatory tumor biopsies to assess EWS-FLI1 target blockade by mithramycin (see [Appendix 7: Studies to be performed on tumor tissue](#)).

Mithramycin will be administered intravenously over 6 hours once daily for 7 days to be repeated every 28 days. Patients may continue to receive mithramycin for as long as they tolerate drug (Sections [3.1.1](#) and [3.4](#)) and do not have progressive disease (Section [6.2](#)).

Patients on study will be closely monitored for the development of toxicity including regular physical examinations, blood pressure monitoring, laboratory evaluations, and physical examinations with particular attention to the development of any signs of bleeding. Patients will be admitted to the hospital for the first treatment cycle during administration of mithramycin in order to allow for close monitoring of toxicities.

Disease will be monitored after every even treatment cycle using appropriate imaging studies using RECIST criteria.

Correlative studies are described in Section [5](#).

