7.3.2 Annual Reporting of AEs to the Sponsor

7.4 FDA REPORTING CRITERIA

7.4.1 IND Safety Reports to the FDA (Refer to 21 CFR 312.32)

The Sponsor will notify the FDA of any unexpected fatal or life-threatening suspected adverse reactions as soon as possible but no later than 7 calendar days of initial receipt of the information using the MedWatch Form 3500a.

The Sponsor is also responsible for reporting:

- any suspected adverse reaction that is both serious and unexpected;
- any findings from clinical, epidemiological, or pooled analysis of multiple studies or any findings from animal or in vitro testing that suggest a significant risk in humans exposed to the drug;
- clinically important increase in the rate of a serious suspected adverse reaction over that listed in the protocol or investigator brochure;

to the FDA and to all investigators no later than 15 calendar days after determining that the information qualifies for reporting using the MedWatch Form 3500a. If FDA requests any

additional data or information, the sponsor must submit it to the FDA as soon as possible, but no later than 15 calendar days after receiving the request.

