7.5 DATA AND SAFETY MONITORING PLAN

7.5.1 Principal Investigator/Research Team

The clinical research team will meet on a regular basis, biweekly when patients are being actively treated on the trial to discuss each patient in detail. The PI will meet regularly with participating site investigators during study enrollment and treatment. Decisions about dose level enrollment and dose escalation during the phase I portion will be made based on the toxicity data from prior patients.

All data will be collected in a timely manner, entered into C3D and reviewed by the principal investigator or a lead associate investigator in a timely manner. Adverse events will be reported as required above. Any safety concerns, new information that might affect either the ethical and or scientific conduct of the trial, or protocol deviations will be immediately reported to the IRB using iRIS and to the Sponsor.

The principal investigator will review adverse event and response data on each patient to ensure safety and data accuracy. The principal investigator will personally conduct or supervise the investigation and provide appropriate delegation of responsibilities to other members of the research staff.

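### Phase II has one enrollment hold for toxicity, limited to hepatotoxicity in the first 6 patients; severe bleeds, non-hepatic drug deaths and drug deaths after patient 6 require no pause.

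*Combined protocol and SAP*

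**What the plan says.** The phase II hold is at the end of section 3.3: "If 2 or more of the initial 6 patients enrolled at the 17.5 mcg/kg dose experience dose-limiting hepatotoxicity, enrollment will be put on hold", pending discussion with the sponsor, the IRB and possibly FDA.

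Severe bleeding is handled patient by patient. Sections 3.3 and 3.7.1 stop mithramycin permanently for a patient with, among other events, "grade 3 hemorrhage if endoscopic or operative intervention required or any grade 4 hemorrhage", CNS hemorrhage of any grade, or a bleed of grade 2 or more that does not resolve within 6 hours of treatment. Section 3.1.1 makes the listed toxicities treatment limiting in phase II, which again concerns the individual.

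The background ranks the risks. Section 1.2.3 states: "The most profound toxicity seen was hemorrhage". It describes bleeding as dose related, "occurring in 5.4% of 1150 patients treated at 30 mcg/kg/day or less", and cites 3 deaths among 84 patients in early reports. Appendix 1, in the package insert row, gives a drug mortality of 1.6% at 30 mcg/kg/day or less.

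Other safeguards are in place:
- Section 2.1 excludes active bleeding, bleeding diatheses, most anticoagulation and NSAIDs, and requires normal PT/PTT and adequate fibrinogen.
- Section 3.1: "Patients will be admitted to the hospital for the first treatment cycle".
- Section 4.1 sets a bleeding work-up and platelet support.
- Sections 7.2.1, 7.3.1 and 7.4.1 set expedited reporting. This includes sponsor notification to FDA of a "clinically important increase in the rate of a serious suspected adverse reaction over that listed in the protocol or investigator brochure".
- Section 7.5.1 has a biweekly case review and immediate reporting to the IRB and sponsor of "Any safety concerns, new information that might affect either the ethical and or scientific conduct of the trial".

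**The concern.** The hold covers one organ and ends at patient 6. With 24 evaluable patients, that leaves 18 (75%) under no written toxicity hold. Patients added for biopsies are in the same position, since section 3.1.3 says "enrollment on this trial will continue for patients undergoing tumor biopsies until a minimum of 12 patients" have evaluable tissue.

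If a phase II patient dies of a drug-related hemorrhage, or several have severe bleeds, the protocol requires reports but not a pause. The pause then rests on the judgment of the investigators, sponsor or IRB at the time. Section 8.6 expects 1 to 2 patients a month over both portions, so the team will learn of each event quickly under either arrangement. What is missing is certainty that enrollment waits for the outside discussion. The sponsor has already accepted that principle for hepatotoxicity.

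**Working it through.** **1. Is there another hold?** The places where one could sit:

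| Section | What it does | Requires a phase II pause? |
|---|---|---|
| 3.1.2 | Stops enrollment at 2 or more DLTs in 6 at dose level -1 | No, phase I only |
| 3.3, 3.7.1 | Stops drug for the patient who bleeds | No |
| 3.3, last paragraph | Hepatic DLT, 2 of first 6 | Yes, the only one |
| 7.2.1, 7.3.1, 7.4.1 | Reports deaths and serious events | No |
| 7.5.1 | Reviews and reports; ties enrollment decisions to toxicity for phase I only | No |
| 8.2 | Simon rule, for lack of response | Not for toxicity |
| 8.2.1 | Tabulates toxicity | No |

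**2. The plan's own stopping figure.** Section 8.2 gives a 63% chance of early termination under the null. With 0 responses in 9 at a 5% response rate, 0.95^9 = 0.630, so it reproduces. Expected size is 9 + 15 × 0.370 = 14.5. The hepatic rule has no stated operating characteristics. From 1 − [(1−p)^6 + 6p(1−p)^5], it holds with probability 3%, 11%, 34% and 58% at true hepatic DLT rates of 5%, 10%, 20% and 30%.

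**3. How likely are the uncovered events?** Assumed rates: b = 5.4% any bleed (section 1.2.3) and d = 1.6% drug death (Appendix 1), or half of each. The halving is only illustrative, not a documented lower bound.

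- At least one drug death, 1 − (1−d)^n. For n = 24: 1 − 0.984^24 = 0.321; at half the rate, 1 − 0.992^24 = 0.175. For n = 9: 0.135 and 0.070. Weighted by the Simon early stop: 0.630 × 0.135 + 0.370 × 0.321 = 0.204, and 0.109 at half.
- Bleeds of any grade in 24: expected 24 × 0.054 = 1.3. The chance of 2 or more is 1 − [(1−b)^24 + 24b(1−b)^23] = 0.375, or 0.136 at half the rate.
- Severe bleeds: the 5.4% covers all bleeds. If a quarter or half are severe (1.35% or 2.7%), 2 or more in 24 has probability 0.041 or 0.136.

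**4. How would the added triggers behave?**

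- Death trigger alone: it holds with the probabilities of a drug death in step 3.
- Death, or a second patient with a severe bleed, treating deaths and severe bleeds as separate events with severe-bleed rate s: 1 − [(1−s−d)^24 + 24s(1−s−d)^23]. With d = 1.6%:
  - s = 1.35%: 1 − (0.487 + 0.163) = 0.350
  - s = 2.7%: 1 − (0.348 + 0.236) = 0.416
- If the true severe-bleed rate were 10% or 20%, a second-patient trigger would hold by patient 24 with probability 0.708 or 0.967 (by patient 9: 0.225 or 0.564).

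Under the current text, severe bleeds have probability 0 of forcing a pause at any rate. So do non-hepatic drug deaths and drug deaths after patient 6.

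**The case against.** **Hepatic deaths.** A reader might infer that no number of drug deaths can force a pause. That is too strong. A fatal related hepatic event meets the non-hematologic DLT definition in 3.1.1, so two among the first 6 patients would trigger the hold.

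**Existing oversight.** A reader might also infer that bleeding is unmonitored. The documents contradict that. Entry criteria, inpatient first-cycle dosing, the bleeding work-up and rapid reporting are substantial at a single institution with slow accrual, and anyone in the chain may still pause. This objection stands, and it reduces the point to a required versus a discretionary pause.

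**Historical rates.** They come from doses up to 30 mcg/kg/day, with supportive care that section 1.2.3 calls unclear and without this trial's exclusions. The 1.6% sits in a run-together table cell. Appendix 1 mentions hemorrhage on a second course in one early series, which might suggest late cumulative bleeding. The same row notes no deaths at 25 mcg/kg by continuous infusion and that 50 mcg/kg was tried, without giving the dose for the later bleeds. Section 1.2.3 reports finding no investigation of cumulative toxicity. I therefore place no weight on late bleeding.

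**A crude bleeding trigger.** Counting all bleeds that meet the permanent-stop criteria would include slow-resolving grade 2 events and bleeds from the mandatory day-4 biopsy. If every bleed counted at 5.4% and 1.6%, enrollment would be held at least once in 24 patients with probability 48% to 58%, in people without a curative option. If each later bleed triggered a new hold, about 0.94 holds would be expected. This stands, and it is why the bleeding trigger below is narrower.

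**Deliberate targeting.** Dexamethasone prophylaxis (4.3) and the dose change noted in 8.2 are consistent with a rule aimed at the liver on purpose. Section 1.2.6 was not in the text available for review and may explain it. That would justify the hepatic rule, but not by itself the absence of a hold after a drug-related death.

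**Conclusion.** The point holds in limited form and is a matter for the sponsor to consider, with medium confidence. In the available text, the sole phase II toxicity hold counts hepatic DLTs in the first 6 patients at 17.5 mcg/kg. Severe bleeds, non-hepatic drug deaths and drug deaths after patient 6 leave any pause to discretion.

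On the assumed historical rates, the chance that such a gap matters through at least one drug death in 24 patients is about 32%, or 18% at half the rate. These figures include hepatic deaths in the first 6 patients, which the present rule partly covers. Lower true rates at 17.5 mcg/kg would reduce them; counting deaths judged only possibly related could raise them. The case for a hold after a drug-related death is firm. The exact bleeding threshold is open to debate.

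The documents do not support reading this as evidence that the trial is unsafe, or that events would go unnoticed.

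**What to change.** Keep the hepatic 2-of-6 rule and add to section 3.3: 'At any time in the phase II portion at 17.5 mcg/kg, in any cycle and including biopsy-extension entry, a death possibly, probably or definitely related to mithramycin will put enrollment on hold until a discussion with the sponsor and IRB and possibly FDA has been held.'

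A matching hold is recommended when a second patient has mithramycin-related severe hemorrhage: grade 3 needing endoscopic or operative intervention, any grade 4, or any CNS hemorrhage. Exclude slow-resolving grade 2 bleeds and bleeds attributed only to biopsy or tumor. After each discussion the sponsor should set the count that triggers a further hold, so that enrollment does not stop at every later bleed. The 17.5 mcg/kg limit keeps out the two earlier patients treated at 25 mcg/kg (8.2).

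The biweekly meeting in 7.5.1 can do the counting; no new committee, visit or test is needed. The cost is temporary holds. In 24 patients, the death trigger alone would hold with probability about 32% at a 1.6% death rate and 18% at 0.8%. With the bleeding trigger added, it is about 35% to 42% at a 1.6% death rate, if a quarter to half of bleeds at 5.4% are severe and deaths are separate. Accrual that ends at 9 patients lowers the death-trigger figures to 14% and 7%. If biopsy extension took the total to 36 (an assumption), they would be 1 − 0.984^36 = 44% and 1 − 0.992^36 = 25%. Each hold is a pause for discussion, and at 1 to 2 patients a month a short one should delay few enrollments.
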